3.2.2 Secondary Outcome Measures

1. Neurological sequelae in survivors, assessed at 1, 6, and 12 months after randomization via the Malawi Developmental Assessment Tool (MDAT) for participants up to the age of 59 months old, and the Kaufman Assessment Battery for Children, Version II (KABC II) for participants over the age of 59 months. All survivors will also be assessed using the Glasgow Outcome Scale (GOS)²⁴⁷. The GOS is a global scale for functional outcome that rates patient status into one of five

categories: dead, vegetative state, severe disability, moderate disability or good recovery.

2. Surrogate measures of increased brain volume: At the time of admission (only): opening CSF pressure, archived samples of blood, urine and CSF. Daily while comatose: ophthalmoscopy for papilledema (present/absent), optic nerve sheath diameter in mm, NIRS measurements of cerebral oxygenation and muscle reperfusion, standardized neurologic observations.
3. Standard TCD phenotypes: microvascular obstruction, hyperemia, vasospasm, low flow, isolated posterior hyperemia). Potential mechanisms: increased brain volume per MRI/ischemic changes, hypercapnia/acidosis/seizures, localized ischemia on MRI, compromised hemodynamics/diminished compensatory reserve/increased brain volume per MRI

4 STUDY DESIGN

This clinical trial is a single site, prospective, open, randomized controlled study in which the impact on final outcome of two different, adjunctive therapeutic approaches aimed at reducing increased brain volume or ameliorating its effect on ventilatory status in Malawian children with CM and severely increased brain volume per MRI will be evaluated.

Children who meet the World Health Organization (WHO) clinical case definition of CM (peripheral *P. falciparum* parasitemia of any density, Blantyre Coma Score (BCS) ≤ 2 , and no other discernible cause of coma) will be admitted to the Pediatric Research Ward (PRW) at Queen Elizabeth Central Hospital (QECH) in Blantyre, Malawi, and will be eligible to be screened for participation in the trial. All children whose parents/guardians' consent for screening will undergo ophthalmoscopy and MRI.

- Those without MRI evidence of increased brain volume will be cared for on the PRW, and will contribute to Secondary Objective #2, identifying surrogate markers of increased brain volume and to Secondary Objective #4, establishing association between specific pathogenic mechanisms and each TCD-derived phenotype.
- Children with clinically defined CM and increased brain volume are eligible to be randomized; those whose caregivers consent to screening but decline to participate in randomization will undergo continuous monitoring on the PRW as required for HRV analysis, and will contribute to Secondary Objective #2, identifying surrogate markers of increased brain volume. They would be eligible for rescue ventilation in the event of a respiratory arrest.
- Children with or without evidence of malarial retinopathy (see Section 2.1.1.7) and with evidence of increased brain volume per MRI (see Section 8.2.2.2 and 2.3.3) will be eligible to be randomized and participate in the clinical trial. If the parents/guardians grant informed consent, each participant will be randomized to one of three arms:

Arm 1: Usual care plus immediate ventilatory support (VENT)

Arm 2: Usual care plus hypertonic saline (HPS)

Arm 3: Usual care (UC)

Participants will be monitored as follows:

- PICU-specific monitoring
 - Continuous monitoring of heart rate and rhythm from EKG, respiratory rate, and pulse oximetry via monitor, and blood pressure via arterial line or cuff. Signals will be archived for offline analyses aimed at identifying heart rate variability patterns over time associated with CM and with clinical improvement or decline in association with treatment.

- Electrolytes and acid-base balance 3-hourly during the first 24 hours and 6-hourly thereafter (in those randomized to hypertonic saline)
- PRW and PICU
 - 2-hourly assessments of vital signs (including temperature) and Blantyre Coma Score until BCS = 5 and temperature is $\leq 37.5^{\circ}\text{C}$ for 24 hours, then 6-hourly.
 - 6-hourly assessments of malaria parasitemia and hematocrit, until two consecutive parasitemia counts are negative.
 - 12-hourly neurological examinations,
 - Daily ophthalmoscopy while unconscious
 - Daily ONSD measurements (while unconscious)
 - Daily TCD examinations
 - Daily MRI examinations (while unconscious if participant is clinically stable for transportation to undergo neuroimaging)

The primary objective (treatment success or failure) will be determined within the first 7 days of hospitalization (Figure 8)

Secondary objectives (Figure 8)

1. The secondary objective involving neurological sequelae at 1, 6, and 12 months after randomization will be determined in survivors randomized in the clinical trial.
2. The secondary objective of identifying surrogate measures of increased brain volume will include participants in the clinical trial as well as study subjects who are screened but do not meet inclusion criteria for clinical trial enrollment e.g. their brain volume is not increased enough to qualify for enrollment in the trial and are therefore not randomized.
3. The secondary objective of assessing the safety of early intubation and mechanical ventilation will include participants in the clinical trial as well as study subjects with CM who are screened but do not meet inclusion criteria for clinical trial enrollment e.g. their brain volume is not increased enough to qualify for enrollment in the trial and are therefore not randomized.
4. TCD endpoints will be determined on all participants (see section 7.2.2.4)]

Choice of participant population and sample size considerations

By focusing on children with CM who have severely increased brain volume per MRI, the study population represents those at highest risk of dying of CM. The mortality rate of retinopathy-positive children with severely increased brain volume is 37%.

Prior to study commencement and based on recruitment patterns over the previous five years (the years that the MRI has been available for characterizing brain volume) we expected to enroll approximately 30-35 retinopathy-positive and 10-12 retinopathy-negative participants with severely increased brain volume per year.

The rate of participant enrollments has decreased, and challenges have been faced in almost all study years:

- 2017: the pediatric intensive care unit remained under construction. Given a steady decline in enrollment rates for pediatric cerebral malaria on the Research Ward, a referral network of 6 hospitals within an hours' drive of the Queen Elizabeth Central Hospital was established. No participants were recruited or randomized.
- 2018: The Malawi Pharmacy, Medicines and Poisons Board unexpectedly delayed the clearance needed to import 3% hypertonic saline (HPS). Protocol amendments were made quickly. Fifty-seven participants were recruited, and 8 were randomized: 4 to usual care and 4 to ventilatory support.
- 2019: The inability to import 3% HPS to Malawi continued. A total of 42 participants were screened, and 24 were randomized (12 to ventilatory support and 12 to usual care).
- 2020: The MRI scanner became non-functional and repair efforts were stymied by the adverse impact of the COVID-19 pandemic on international travel. (The repair technician could not travel from South Africa to Malawi after all commercial flights to Malawi ceased.) A total of 48 patients was screened, but none were randomized because brain volume could not be assessed. We will have a new, low field MRI machine (manufactured by Hyperfine) capable of assessing brain volume in place for the 2021 season.
- 2021: A low field MRI machine (manufactured by Hyperfine) capable of assessing brain volume was placed in service in late March 2021. The possibility of randomization was delayed until after the portable MRI became functional.
 - a. Given these successes and challenges and the potential beneficial effects on mortality described in Section 11.2, a study comparing two interventions to Usual Care that will answer our original research questions prior to study closure will be challenging but remains feasible. Answering the question whether mechanical ventilation or intravenous hypertonic saline decreases mortality risk in children with CM requires sing participants enrolled in the BMP observational study prior to clinical trial commencement as Historical Controls (obviating the need for randomizing high numbers of participants into the Usual Care arm)

Historical Controls:

We identified potential Historical Controls from the electronic database of the completed observational study of cerebral malaria pathogenesis. In order to minimize temporal differences between participants randomized in the clinical trial, we began our search with children enrolled in the observational study in 2017 and moved backwards in time.

Neuroradiologists affiliated with the Treating Brain Swelling clinical trial assessed the brain MRI scans on over 200 children enrolled in the observational study. These images dated from 2014-2017.

Once consensus brain volume scores on these MRI scans were assigned by the neuroradiologists, we retrieved demographic and clinical data on children who had assigned brain volume scores of 6-8 from the master Blantyre Malaria Project database. Demographic, clinical, and outcome data were compared between children enrolled in the observational study who had brain volume scores of 6-8, and children randomized in the Treating Brain Swelling clinical trial and were randomized to Usual Care with the same range of brain volume scores. Comparisons were made between the following variables: age (in months), sex, Blantyre coma score, admission glucose, admission hematocrit, admission platelet count, and outcome. Statistical analysis: Comparisons between groups were made using t-tests or Wilcoxon test (continuous variables), ANOVA (categorical variables), or chi squared tests (dichotomous variables), as appropriate.

We found no difference in the variables in question between children enrolled in the observational study who had MRI brain volume scores of 6-8, and participants randomized in the clinical trial who had MRI brain volume scores of 6-8.

Table 4. Continuous variables compared between historical controls and randomized study participants

Variable	OS mean	OS SD	TBS mean	TBS SD	P value
Age (months)	48.25	27.54	59.63	27.88	0.168
Glucose	5.87	2.94	5.63	3.13	0.914 ^d
Hematocrit (%)	23.36 ^a	6.29	25.54	6.97	0.555 ^d
Platelets (*1000/MicroL)	148.9 ^b	373.7	94.3 ^c	176.2	0.993 ^d

OS= observational study (n=48), SD= standard deviation, TBS= treating brain swelling clinical trial (n=16)

^a n=45, ^b n=47, ^c n=15. ^d nonparametric test.

There was no significant difference in admission Blantyre Coma score (p=0.948), sex (p=0.885) or outcome (death/survival, p=0.551) between the 48 children in the observational study and the 16 randomized participants in the Treating Brain Swelling clinical trial.

We therefore conclude that participants enrolled in the observational study (n=48) are comparable to participants randomized to Usual Care (n=16) in the Treating Brain Swelling clinical trial.

We anticipate enrollment in the Usual Care arm in the 2023 season (see below) at a reduced ratio compared to the intervention arms.

Possible future declaration of futility of the ventilation arm:

If we combine the mortality risk in Historical Controls and participants already randomized to Usual Care, the mortality risk of the combined historical control group and children randomized to Usual Care is 36%. At the end of the 2021 season, the mortality risk in the VENT arm was 26.3%. (Five of 19 participants randomized to VENT died or were brain dead.) With only these data, the test of the null hypothesis of a null difference in mortality is not significant (p-value 0.818, 2-sided test).

We believe it likely that VENT will, in the future, be declared futile. If so, randomization of participants enrolled in the Treating Brain Swelling clinical trial after the declaration of futility of VENT would be to HPS or UC. A formal approach to futility assessment for VENT is provided below.

Table 4. Projected enrollment

	2018 – 2021	2022	2023	Total
*Usual care (UC)	64	0	4	68
Ventilatory support (VENT)	19	7	6	32
Hypertonic saline (HPS)	3	14	15	32

*historical controls + study participants enrolled in 2018 and 2019.

Assuming that enrollment in 2023 follows the same trend seen since the beginning of the clinical trial, we will be able to detect a 50% or more risk reduction in either the VENT or HPS arms, compared to UC.

Choice of interventions

The three study arms of the study will be:

1. Arm 1: Usual care + immediate mechanical ventilatory support (VENT) for a maximum of 7 days, with ventilator withdrawal once brain volume has decreased (brain volume score ≤ 5) or the patient has improved clinically (modified Blantyre Coma Score ≥ 3) or the patient dies or meets criteria for severe irreversible neurologic failure.
2. Arm 2: Usual care + intravenous hypertonic saline (HPS) for a maximum of 7 days, withdrawn once brain volume has decreased (brain volume score ≤ 5) and the patient

has improved clinically (Blantyre Coma Score ≥ 3) or the patient dies or meets criteria for severe irreversible neurologic failure.

3. Arm 3: Usual care (UC); intravenous fluids, intravenous artesunate; antipyretics, anticonvulsants and blood transfusions as needed; nutritional support) for a maximum of 7 days, or until brain volume has decreased (brain volume score ≤ 5) and the patient has improved clinically (Blantyre Coma Score ≥ 3) or the patient dies or meets criteria for severe irreversible neurologic failures

Participants will remain in the study throughout their hospitalization and, in survivors, through the 12-month post-randomization follow-up visit. Children are discharged when two sequential 6-hourly blood films are free of malaria parasites, when they have been afebrile for 24 consecutive hours, and when they are able to take medications and food by mouth. Final data collection will be at 12 months post-randomization.

Stratification:

No stratification is required. The ages of retinopathy-positive CM with severely increased brain volume per MRI who survived were compared to those of participants from the same population that died. There was no difference in the age structure (data not shown, $p=0.95$).

Primary and secondary outcomes.

The primary outcome is treatment success or failure, determined within the first 7 days. Treatment success is recovery. Treatment failure is death, ventilatory rescue (for participants in Arms 2 and 3) or meeting criteria for severe irreversible neurologic failure.

The secondary outcomes include rates of neurological sequelae in all 3 groups; potential surrogate measures of increased intracranial pressure (opening CSF pressure, ONSD measurements from serial ultrasound examinations, NIRS measurements of cerebral oxygenation and muscle reperfusion, serial examinations for papilledema, decreased diastolic flow velocity or increased pulsatility index on TCD, heart rate variability patterns from continuous cardiac monitoring measured from enrollment through initial MRI scan, and standardized clinical observations) and development of hypotension following induction/intubation, defined by proportional deviation from the initial systolic blood pressure at enrollment.

Data collection methods.

The primary outcome will be determined by study clinicians.

For secondary objectives, the following methods will be used:

- ONSD measurements will be collected at the bedside. Data will be transferred to the electronic case report form (CRF).

- TCD measurements will be collected at the bedside. Data will be transferred to the electronic case report form (CRF).
- NIRS will be used to record cerebral oxygenation fluctuations and to measure muscle reperfusion rates after transient occlusion.
- The evolution of heart rate variability and its relationship to clinical status and outcomes will be determined by extracting the archived and time-stamped continuous ECG signal.
- The neurological findings will be captured by clinicians on an electronic case report form (CRF) at the bedside.
- Neurologic status at the 1, 6, and 12-month post-randomization follow-up will be assessed by one of two pediatric neurologists or clinicians trained by them. The Glasgow Outcome Scale (GOS), a global scale for functional outcome that rates patient status into one of five categories (dead, vegetative state, severe disability, moderate disability or good recovery)²⁴⁷ will be used.. Study nurses will administer standardized assessments: The Malawi Developmental Assessment Tool (MDAT) for participants up to the age of 59 months; the Kaufman Assessment Battery for Children, Version II (KABC-II), for participants over the age of 59 months. Both have been validated for use in African children ^{248, 249}.

The details of the techniques involved for the specialized assays (funduscopy, MRI, ONSD, TCD, NIRS, heart rate variability) are included in Section 8 of this Protocol.

Centralization of evaluations: MRI, ophthalmoscopy, ONSD, TCD, EEG, and neuro-checks will be carried out either at the bedside in the PRW/PICU or in the MRI suite.

Safety monitoring: A local independent safety monitoring team (ISM) will be appointed for the study. The team will consist of two local physicians with knowledge of the clinical setting and practices, but without direct involvement with this study. They will be notified of all SAEs and asked to comment on the relatedness of these events to the interventions. They will also be asked to review AEs at the discretion of the local investigators, IRBs, or the Data Safety and Monitoring Board (DSMB).

A DSMB is justified for this study for two reasons: (1) the anticipated mortality in this group of gravely ill children, without adjunctive treatment, is over 30% (2), and serious adverse events have been reported for HPS (Section 2.3.1.2) and assisted ventilation (Section 2.3.1.3). Interventions may result in survival of children who would have otherwise died, and some of these children may be severely neurologically impaired. In a country like Malawi where there is no social support for such children and their families, their survival could create a burden for the family which might worsen stress and social problems.

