scores of 7 (and therefore were eligible for randomization in real time) had consensus scores of 6. Three subjects with real-time assignment of brain volume scores of 6 had a consensus score of 7.

Comparisons between brain volume scores assigned in real time and the consensus score showed that for scores of 6 or less, neuroradiologists interpreting images in real time generally assigned brain volume scores higher than the consensus score. During the first enrollment season, a score of 5 or 6 was assigned 17 times in real-time. Adjudicated scores were the same (4), lower (12), or higher (1). One subject assigned a brain volume score of 5 had an adjudicated score of 7.

To include all participants who should be randomized (e.g. that have an adjudicated brain volume score of 7 or 8) requires that all participants with brain volume scores of ≥ 6 are eligible for randomization. To try to avoid including participants who will eventually have an adjudicated score of 5 or less, beginning in the 2019 enrollment season, all participants will have 2 independent MRI interpretations for brain volume score performed in real-time. If both real-time interpretations have a brain volume score of ≥ 6 the participant will be eligible for randomization. If either of the independent real-time neuroradiologists assigns a brain volume score of < 6 the participant will not be eligible for randomization.

Beginning in 2021, the 0.35T fixed magnet General Electric MRI will be replaced with a portable MRI scanner manufactured by Hyperfine. Clinical trial participants may be scanned with the 0.35 T General Electric MRI machine, the Hyperfine scanner, or both.

Interventions

Our site, by virtue of its ready access to MRI and pediatric intensive care, is uniquely qualified to identify the study population and carry out the clinical trial. For the findings to be useful in other malaria-endemic settings, it will be important to identify and validate more user-friendly approaches to identifying children with life-threatening increases in brain volume, and to determine the simplest approach to treat them. These dual objectives are the basis of the primary and secondary aims of the study.

Criteria for selecting experimental interventions

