5.3 Treatment Assignment Procedures

5.3.1 Randomization Procedures

The study will be randomized, but not blinded. Participants will be randomized after completing the eligibility screening procedures. A block randomization scheme will be used to ensure groups of equal size. Blocks sizes of six and nine will be rotated to decrease the predictability of group allocation within a block for data collectors. Children with retinopathy-positive CM will be randomized separately from those with retinopathy-negative CM.

Randomization is based on obtaining a consensus interpretation of brain volume per MRI. If this is not possible for any reason, study participants will be screened but not randomized, and will remain on the PRW. All other study procedures will be followed as described in this protocol.

Randomization is predicated on the risks and benefits as described in this protocol. Endotracheal intubation is required for participants randomized to the “intubation + mechanical ventilation” arm. The current coronavirus pandemic affects the risk/benefit ratio of this arm of the study because endotracheal intubation increases the risk of aerosol spread of the coronavirus (US CDC COVID19 guidance, 4.4.20, www.cdc.gov/coronavirus/2019-ncov/hcp/guidance-risk-assesment-hcp.html). Randomization to the mechanical ventilation arm will be adjusted in accordance with local IRB recommendations during the coronavirus pandemic.

All possible blocks with balanced combinations of group assignment will be documented. Next computer-generated random numbers will be used to select from the balanced blocks. Assignment of study subjects to randomization arm will be performed electronically, through the online data capture mechanism. If Internet service is unavailable at the time of randomization, back up sequentially numbered opaque sealed envelopes prepared before the trial begins will be available. The envelopes will be stored in a secure location with access limited to key study personnel. After a caregiver provides consent for a patient to participate in the study, study arm assignment will first be attempted electronically. If Internet service is unavailable, study personnel will open the next unopened sequentially numbered envelope to reveal the group assignment and dosing calculation sheet.

A master log of all screened and enrolled subjects will be maintained. A subject is considered randomized upon online assignment or opening the envelope to indicate treatment assignment.

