8.3.2 MRI

MRI of the brain will be the “gold standard” for assessing the presence of brain volume. The final determination of brain volume will be made initially by one of two experienced radiologists. They will use the following scale⁵²:

1 = severe atrophy markedly abnormal for age with diffuse prominence of the cisternae and sulci

2 = mild atrophy – subtle prominence of the cisternae and sulci for age

3 = normal brain volume

4 = mild increased volume but with maintenance of cisternae and sulci

5 = mild swelling – some loss of cisternae and sulci but not diffuse

6 = moderate swelling – diffuse involvement with some loss of cisternae and sulci

7 = severe swelling – loss of all sulci, presence of cisternal effacement, decreased gray/white matter delineation

[figure not shown]
8 = severe swelling – loss of all sulci, presence of cisternal effacement, presence of uncal herniation, loss of gray/white matter delineation

The presence of severely increased volume (edema score 7 or 8) identifies the subset of children who are most susceptible to herniation and therefore death (Figure 5). Real-time interpretations during the 2018 enrollment season revealed that neuroradiologists could not reliably differentiate a brain volume score of 6 or 7. In order to include all subjects who might benefit from the interventions, subjects with brain volume scores of 6-8 will be eligible for randomization (see Section 2.3.3).

Two study radiologists will be available at all times to review MRIs and assign a brain volume score. If both independently assigned brain volume scores are ≥ 6 , the participant will be eligible for randomization. If either independently assigned, real-time score is < 6 the participant will not be eligible for randomization.

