11.5 Sample Size and Power

For the primary outcome death/failure of the intervention, we conduct two parallel studies: (i) VENT versus control UC, (ii) HPS versus control UC. Approximately 128 children will be enrolled in the studies. This includes the 64 children in UC comprised of 16 randomized to UC in the 2018-2019 malaria seasons and augmented by 48 historical controls from previous seasons (2014-2017). We also randomized 16 children to VENT in the 2018-2019 malaria seasons.

Table 8: Summary of outcome measures and analytic plan		
Outcome measure	Outcome type/scale	Analytic method
PRIMARY OUTCOME		
Success of primary intervention or survival in the first 7 days after randomization	Binary	Logistic regression
SECONDARY OUTCOMES		
Brain volume determination (MRI on admission, then daily)	Ordinal	Ordinal regression
Optic Nerve Sheath Diameter (on admission, then daily)	Continuous	Linear regression. Serial assessments by repeated measures analysis
Transcranial Doppler ultrasound (on admission, then daily)	Continuous	Linear regression. Serial assessments by repeated measures analysis
Opening CSF pressure (mm CSF) (on admission)	Continuous	Linear regression
Heart rate variability patterns	Continuous	Linear regression. Serial assessments by repeated measures analysis
Neurologic exam * (on admission, then twice daily)	21 binary and 5 continuous variables	Linear or logistic regression
Papilledema (on admission, then daily)	Binary	Logistic regression
Severe neurologic sequelae at 16 and 12 months	Binary	Logistic regression. Serial assessments by repeated measures analysis
Hypotension that occurs within 30 minutes of sedation administration, initiation of mechanical ventilation or ventilator pressure adjustment.	Binary	Logistic regression.

Since the beginning of this study, we faced several logistical challenges but had success in recruiting 32 children in 2018-2019 (16 each in VENT and UC). Based on our current data, the estimated mortality in UC and VENT are respectively, 36% and 25%. Maintaining the mortality rate in UC, a one-sample lower test at significance level $\alpha=0.05$ of a null difference has 80% power to detect a reduction in mortality to 18% in VENT with 33 subjects in VENT.

[figure not shown]

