11.6 Interim Analyses

The TBS design is a 4-stage sequential plan to compare VENT to UC on the outcome of mortality. Based on historical controls and initial randomization to UC before 2020, mortality is

assumed fixed at $p_0 = 0.28$. We test the hypothesis that mortality p in VENT is lower, i.e., we test $H_0 : p = p_0$ versus $H_1 : p < p_0$ at significance level $\alpha = .05$. VENT will be declared superior to UC, if we can demonstrate a relative risk reduction of 50% with 80% power. This needs a sample of 38 subjects.

Boundaries for the 4-stage plan are derived from the power family. Early stopping is to reject the null hypothesis. Our first interim analysis was conducted with data from the 2019-2020 malaria seasons. Observed mortality in VENT was 12.5% (2/16). The conclusion was to continue to the next stage. Our current estimate, at the end of the 2021 season is 15.8% (3/19). In accordance with the design, we must continue to the next stage (i.e., 2022 season). The revised boundary information is depicted in the figure.

Figure: Boundary plot at conclusion of stage 2

Legend: The scale is the maximum likelihood estimate (MLE) of the mortality difference (PDIFF), $\theta = p - p_0$ against the actual information level. At stage 1, observed $\theta = 0.125 - 0.28 = -0.155$, and at stage 2, $\theta = 0.158 - 0.28 = -0.122$. The rejection boundaries are not crossed.

Conditional power and predictive power

Conditional power (CP) is the power to reject the null hypothesis $H_0: \theta = 0$ at all future stages given the cumulative interim data. This calculation shows: (a) at the current estimated difference in mortality $\theta = -0.122$, CP=76.1%, (b) at zero difference in mortality, CP=18.6%, (c) at the hypothesized difference, $\theta = -0.14$, CP=82.9%. Predictive power (PP) is the posterior probability

of rejecting the null at the next stage given the current data, assuming a non-informative prior on the mortality difference. PP=66.1% at the current stage.

Based on these assessments it behooves that we proceed to stage 3.

Hypertonic saline (HPS) vs UC

We have our first sample of 3 subjects, one of whom died. Although hardly necessary, a formal analysis provides the exact 95% CI for mortality in HPS, (0.008, 0.906).

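### Three quarters of usual care is historical on a weak comparability check; the plan gives two methods for the primary outcome, no test for HPS in Section 11.6, and two control rates

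*Combined protocol and SAP*

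**What the plan says.** **Who the controls are.** Section 11.5 describes the UC group: "This includes the 64 children in UC comprised of 16 randomized to UC in the 2018-2019 malaria seasons and augmented by 48 historical controls". The Historical Controls text in Section 4 says how the 48 were found: "Once consensus brain volume scores on these MRI scans were assigned by the neuroradiologists, we retrieved demographic and clinical data on children who had" scores of 6-8.

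**How trial children qualify.** From 2019, Section 2.3 says "all participants will have 2 independent MRI interpretations for brain volume score performed in real-time", and Section 8.3.2 adds "If either independently assigned, real-time score is < 6 the participant will not be eligible for randomization". Section 5.3.1 instead says "Randomization is based on obtaining a consensus interpretation of brain volume per MRI".

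**Comparability.** Section 4 compares the 48 with the 16 randomised UC children on age, sex, coma score, glucose, hematocrit, platelets and outcome, finds no significant difference, and concludes that they are comparable. Section 11.2 says mortality varies by retinopathy status, which is not among those variables.

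**Primary analysis.** Section 11.6 opens with "The TBS design is a 4-stage sequential plan to compare VENT to UC on the outcome of mortality" and tests VENT against a control rate fixed at 0.28. Section 11.7 sends the primary outcome to that test and cites Table 8 for secondary outcomes. Yet Table 8 has a primary row, "Success of primary intervention or survival in the first 7 days after randomization", with logistic regression as its method, and the next paragraph of 11.7 says binary outcomes in Table 8 are analysed by logistic regression. Section 11.3 makes covariate adjustment optional.

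**Control rate.** Section 11.5 says "the estimated mortality in UC and VENT are respectively, 36% and 25" percent; Section 4 also gives 36% for combined UC. Section 11.6 uses 0.28 for a control group described in the same way.

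**The concern.** A test against a fixed control rate has no protection from differences between the children who supplied that rate and the children treated. Any difference in retinopathy, swelling score, calendar time or scanner (Section 2.3 replaces the machine from 2021) enters the treatment effect unadjusted. The logistic regression could adjust for measured factors, but the plan does not require it to and gives no order of precedence if the two methods disagree.

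HPS is the most exposed. Its 32 children are compared almost wholly with children treated in other years, and Section 11.6 offers only a confidence interval from the first three. The two control rates matter separately, because they set different bars for declaring VENT superior.

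**Working it through.** **1. The plan's own figures.**
- Section 11.6, one-sample test, 0.28 to 0.14, one-sided alpha 0.05, power 80%, variance at the alternative: n = (1.645 + 0.842)² × 0.14 × 0.86 / 0.14² = 37.98, so 38. This matches.
- The 33 in Section 11.5 (0.36 to 0.18) is not reproduced by that formula, which gives 28.2. Nothing below depends on it.
- Age in Section 4: difference 59.63 − 48.25 = 11.38 months; SE = √(27.54²/48 + 27.88²/16) = 8.02; t = 1.42; Welch p = 0.168. This matches. The 95% CI is −4.6 to 27.3 months and the standardised difference 0.41.

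**2. Composition and concurrency** (Sections 4 and 11.5).
- Historical share: 48/64 = 75%, or 48/68 = 71% on the projected total.
- HPS enrolment: 3 + 14 + 15 = 32. HPS could not be imported in 2018-2019 and nobody was randomised in 2020, so the first 3 date from 2021. The randomised UC children to date are from 2018-2019. Projected UC enrolment is 0 in 2022 and 4 in 2023, so at most 4 are concurrent with HPS. Section 11.7 allows for none.

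**3. What the 48-against-16 check can detect.** Full enumeration of two binomials, two-sided 0.05:

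| Historical vs randomised UC | Chi-square | Fisher |
|---|---|---|
| 36% vs 18% | 26% | 22% |
| 36% vs 54% | 25% | 20% |

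For a continuous variable, 80% power requires a standardised difference of about 0.81.

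**4. What p=0.551 for outcome implies.** The split of deaths is not given.
- With Fisher's test, the only split that gives both p=0.551 and a pooled rate of 36% is 16/48 (33%) vs 7/16 (44%). The difference is 10 points, Newcombe 95% CI −15 to +36.
- With the chi-square test that Section 4 names for dichotomous variables, 17/48 vs 7/16 and 19/48 vs 5/16 both give 0.551 (pooled 24/64 = 37.5%). These point in opposite directions, so either sign is possible.

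**5. The control rate.** Single-stage exact one-sided test at n=38, largest count with tail probability at or below 0.05:
- Against 0.28: reject at 5 or fewer deaths (13%); size 0.026. Six or fewer has size 0.062.
- Against 0.36: reject at 8 or fewer deaths (21%); size 0.036.

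The VENT figures shift in parallel. Section 4 has 5/19 = 26.3%, counting deaths and brain deaths, and Section 11.5 has 25%. Section 11.6 has 3/19 = 15.8% and 2/16 = 12.5%.

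**6. Power when the control rate is estimated.** Pooled z, one-sided 0.05, unadjusted, full enumeration:

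| Rates | 64 vs 38 | 64 vs 32 | 16 vs 16 |
|---|---|---|---|
| 0.28 vs 0.14 | 50% | 46% | 24% |
| 0.36 vs 0.18 | 63% | 58% | 29% |

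**The case against.** **Section 11.7 does name a test.** A reader might infer that the plan has no primary test. For VENT that is wrong: 11.7 points to the sequential test and cites Table 8 for secondary outcomes. What stands is the conflict with the primary row in Table 8 and the next paragraph of 11.7, and the absence of an HPS test in 11.6.

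**The reading mismatch is partly handled.** A reader might infer that milder children enter the trial and make treatment look better. Section 2.3 does report that real-time scores of 6 or less generally ran above consensus. But the two-reader rule was introduced to limit this, the per-protocol set in Section 8.3.2 drops children wrongly enrolled by consensus score, and Section 4 restricts the UC comparison to scores of 6-8 (without saying which read). How many trial children fall below consensus 6 is not stated, and the Fisher split has higher mortality in the trial's own UC children. No direction of bias is established. The consensus wording in 5.3.1 may simply mean agreement of the two readers.

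**The two control rates may count different outcomes.** The parallel shift in the VENT figures makes this plausible. It would be wrong to quote an inflated error rate from setting 0.36 against 0.28, because that could mix definitions. The need to reconcile them stands.

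**Retinopathy is not ignored.** Section 11.3 lists it for a comparison across arms, and 2.1.13 plans a sensitivity analysis. But 11.3 compares arms rather than control sources, and 2.1.13 asks whether treatment effects vary by retinopathy status, not whether historical and trial children differ.

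**Conclusion.** The concern holds in this form. Comparability of a control group that is 75% historical rests on non-significance at 20-26% power for an 18-point mortality gap, and the check leaves out a factor the plan itself calls prognostic. Two methods are assigned to the primary outcome without precedence. HPS vs UC has no test in Section 11.6 and at most 4 concurrent controls for 32 children. The control rate appears as both 36% and 0.28, which moves the rejection count at n=38 from 8 to 5.

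The documents do not show that the historical controls bias the result in either direction, or by how much. The rejection counts are single-stage and ignore the four-stage boundaries; they illustrate sensitivity and are not the trial's actual limits. The powers are unadjusted and take the plan's own rates as true.

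**What to change.** 1. Reconcile 36% with 0.28, state which outcome each counts, and use one definition for the control rate and the treated arm.
2. State that the sequential fixed-rate test decides for VENT and correct the Table 8 row to match. Name the logistic regression, adjusted for retinopathy stratum and consensus baseline score, as the deciding analysis for HPS vs UC. Report the same adjusted odds ratio with 95% CI for VENT as a prespecified supporting analysis. Keep all randomised children in both.
3. Tabulate retinopathy, consensus score (6, 7, 8), scanner and 7-day outcome separately for historical UC, randomised UC, VENT and HPS. Report the concurrent 16-vs-16 VENT-vs-UC comparison descriptively.
4. Reconcile Section 5.3.1 with Sections 2.3 and 8.3.2 on which read qualifies a child.

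**Cost.** SAP wording, one regression and one table; the VENT boundaries are untouched. The limits should be stated. Events are few (36% of 64 is about 23 UC deaths). Retinopathy status must be confirmed for the 48 historical children. The two-sample comparison has about 46-63% power rather than 80%, and the 16-vs-16 comparison 24-29%. Adjustment covers only what was measured and cannot replace concurrent controls for HPS.
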